7.3. Other Safety Analyses

The analyses of non-laboratory safety test results including ECGs and vital signs will be based on GSK Core Data Standards, unless otherwise specified. The details of the planned displays are presented in [Table 5](#) below and [Appendix 10: List of Data Displays](#).

7.3.1. Summary Measures

Non-laboratory safety results will be summarised in tables and figures by the following:

- Parts A, B and Follow-up by randomised treatment;
- Parts A, B and Follow-up by period treatment (i.e. treatment participant actually received).

Non-laboratory safety results will be presented in data listings by the following:

- Parts A and B and follow-up by period treatment (i.e. treatment participant actually received).

Table 5 Overview of Planned Other Safety Analyses

Endpoint / Parameter/ Display Type	Absolute			Change from BL		
	Summary		Individual	Summary		Individual
	T	F	L	T	F	L
ECG						
ECG Findings	Y					
ECG Values ¹				Y		
Maximum QTc Values Post-Baseline Relative to Baseline by Category ¹	Y					
Maximum Increase in QTc Values Post-Baseline Relative to Baseline by Category ¹	Y					
All ECG Values for Subjects with Any Value of PCI ¹			Y			
Vital Signs						
Vital Signs				Y		
Worst Case Vital Signs Results by PCI Criteria Post-Baseline Relative to Baseline	Y					
All Vital Signs for Subjects with Any Value of PCI			Y			
C-SSRS V4						
C-SSRS Suicidal Ideation and Behaviour Data			Y			

NOTES:

- ECGs change from baseline are to be produced for change from screening (average triplicate) and change from baseline
 - T = Table, F = Figures, L = Listings, Y = Yes display generated, PCI = Potential Clinical Importance
 - Summary = Represents TFL related to any summaries (i.e. descriptive statistics) of the observed raw data.
 - Individual = Represents FL related to any displays of individual participant observed raw data.

7.4. Other Safety Analyses

If any of the following events are recorded in the eCRF as a CV event during the study, posthoc patient profile listings will be generated per IDSL and provided to the GCSP department:

- Arrhythmias, Congestive heart failure, Cerebrovascular events stroke (CVA) and Transient ischemic attack (TIA), Deep vein thrombosis (DVT)/Pulmonary embolism (PE), Myocardial Infarction/Unstable Angina, Peripheral arterial thromboembolism, Pulmonary Hypertension, Revascularisation, Valvopathy.

8. EFFICACY

8.1. Efficacy Endpoints

Table 6 below provides an overview of the planned efficacy analyses, with full details of data displays being available in Appendix 10: List of Data Displays.

Table 6 Overview of Planned Efficacy Analyses

Endpoint	Absolute							Change from Baseline						
	Stats Analysis			Summary		Individual		Stats Analysis			Summary		Individual	
	T	F	L ^[1]	T	F	F	L	T	F	L ^[1]	T	F	F	L
Mayo – Endoscopy Response														
Mucosal Appearance at Endoscopy Mayo Subscore				Y							Y			
Proportion Achieving Mayo Endoscopy Remission	C	C	C	Y	Y		Y							
Mayo – Clinical Response and Remission														
Proportion Achieving Mayo Clinical Response	C	C	C	Y	Y		Y							
Proportion Achieving Mayo Clinical Remission	C	C	C	Y	Y		Y							
Proportion Achieving 3-domain Mayo Clinical Response	C	C	C	Y	Y		Y							
Proportion Achieving 3-domain Mayo Clinical Remission	C	C	C	Y	Y		Y							
Mayo – Symptomatic Clinical Remission														
Total				Y	Y		Y	C	C	C	Y	Y		Y
Partial Mayo				Y	Y		Y	C	C	C	Y	Y		Y
3-domain Mayo				Y	Y		Y	C	C	C	Y	Y		Y
UCEIS – Mucosal Healing														
UCEIS Total Score				Y	Y		Y	C	C	C	Y	Y		Y
UCEIS – Remission														
Proportion Achieving UCEIS Remission	C	C	C	Y	Y		Y							
Biomarkers of Disease Activity														
CRP				Y	Y		Y	C	C	C	Y	Y		Y
FCP ^[2]				Y	Y		Y	C	C	C	Y	Y		Y
Histologic Disease Activity														
Modified Riley Scale				Y	Y		Y	C	C	C	Y	Y		Y
Geboes Index Total Score				Y	Y		Y	C	C	C	Y	Y		Y
RHI Total Score				Y	Y		Y	C	C	C	Y	Y		Y

Endpoint	Absolute						Change from Baseline							
	Stats Analysis			Summary		Individual	Stats Analysis			Summary		Individual		
	T	F	L ^[1]	T	F	F	L	T	F	L ^[1]	T	F	F	L
Quality of Life														
IBDQ Domains ^[3]				Y			Y				Y			Y
IBDQ Total Score				Y	Y		Y	C	C	C	Y	Y		Y
Subject Symptom Diary Cards														
Diary Card ^[4]				Y			Y							

NOTES:

- T = Table, F = Figure, L = Listing, Y = Yes display generated, C = conditional
 - Stats Analysis = Represents TFL related to any formal statistical analyses (i.e. modelling) conducted.
 - Summary = Represents TFL related to any summaries (i.e. descriptive statistics) of the observed raw data.
 - Individual = Represents FL related to any displays of individual participant observed raw data.
1. Listing of the RAW SAS output from the statistical modelling.
 2. FCP will be log-transformed before determining change from baseline.
 3. IBDQ domains: Bowel Symptoms, Systemic Systems, Emotional Function and Social Function.
 4. Data from diary cards will be transcribed into the eCRF for the 5 days prior to the following visits: Screening, Day 15, Day 29, Day 43, Day 85 and EW.

8.1.1. Population of Interest

Analyses of the Mayo will be based on the Safety, PP and PP + Completers populations respectively.

All other efficacy analyses will be based on the Safety Population only.

8.1.2. Statistical Analyses / Methods

Details of the planned displays are provided in [Appendix 10](#): List of Data Displays and will be based on GSK data standards and statistical principles.

All efficacy data will be summarised for Parts A, B and Follow-up (if applicable) by randomised treatment.

Unless otherwise specified, endpoints / variables defined will be summarised using descriptive statistics, graphically presented (where appropriate) and listed.

8.1.2.1. Statistical Methodology Specification

8.1.2.1.1 Continuous Endpoints

Secondary and Exploratory Endpoint(s)

 • Change from baseline in Total and 3-domain Mayo Score at Day 43 pre-dose and Day 85. • Change from baseline in Partial Mayo Score at Day 15, Day 29, Day 43 pre-dose and Day 85. • Change from baseline in UCEIS Total Score at Day 43 pre-dose and Day 85. • Change from baseline Modified Riley Scale at Day 43 pre-dose and Day 85. • Change from baseline Geboes Index Total Score at Day 43 pre-dose and Day 85. • Change from baseline RHI Score at Day 43 pre-dose and Day 85. • Change from baseline in CRP at Day 43 pre-dose and Day 85. • Change from baseline in Log-transformed FCP at Day 15, Day 29, Day 43, Day 57, Day 71 and Day 85. • Change from baseline in IBDQ Total Score at Day 43 pre-dose and Day 85.

Model Specification

 Continuous endpoints will be statistically analyzed using a Mixed Models Repeated Measures (MMRM) approach. Terms fitted in the MMRM model will include: 
 Fixed Category : Treatment, Day, Treatment*Day Fixed Continuous Covariates : Baseline Score, baseline*Day Repeated Effect : Day The Kenward and Roger method for approximating the denominator degrees of freedom and correcting for bias in the estimated variance-covariance of the fixed effects will be used. An unstructured covariance structure for the R matrix will be used by specifying 'type=UN' on the REPEATED line with a subject=SUBJID option. 
 In the event that this model fails to converge, alternative correlation structures may be considered such as CS or AR(1). Akaike's Information Criteria (AIC) will be used to assist with the selection of covariance structure. Other covariates maybe explored, if deemed appropriate for sensitivity analyses.
Model Checking & Diagnostics

 MMRM model assumptions will be applied, but appropriate adjustments may be made based on the data. Distributional assumptions underlying the MMRM model will be examined by obtaining a normal probability plot of the residuals and a plot of the residuals versus the fitted values (i.e. checking the normality assumption and constant variance assumption of the model respectively) to gain confidence that the model assumptions are reasonable. If there are any departures from the distributional assumptions, alternative models will be explored using appropriate transformed data.
Model Results Presentation - Untransformed

 Point estimates and corresponding 95% confidence intervals will be constructed for the treatment differences (GSK2982772 60mg tid- Placebo), using the residual error from the repeated measures model. Plots of LS means and 95% confidence intervals from the model will be generated for each treatment group by time. For log-transformed data the adjusted back-transformed geometric means and CV will be presented.
Model Results Presentation - Log transformed

 Adjusted geometric means, the mean difference between each dose (test) and the placebo (reference) at each timepoint and associated 95% confidence interval will be constructed using the residual variance The treatment ratios and 95% CI will be calculated by back-transforming the difference between the least square means and associated 95% CI
Sensitivity and Supportive Statistical Analyses

 Non-parametric analyses may be conducted if the normality assumption does not hold. Analyses using different covariance structures may be explored if the unstructured covariance matrix does not converge.

8.1.2.1.2 Binary Endpoints

Secondary and Exploratory Endpoint(s)

 Proportion of participants achieving a Mayo endoscopy remission at Day 43 pre-dose and Day 85. Proportion of participants achieving Mayo clinical response and 3-domain Mayo clinical response at Day 43 pre-dose and Day 85.

 • Proportion of participants achieving Mayo clinical remission and 3-domain Mayo clinical remission at Day 43 pre-dose and Day 85. • Proportion of participants achieving an UCEIS remission at Day 43 pre-dose and Day 85. 				
Model Specification				

 • Binary efficacy endpoints will be statistically analysed using a Generalised Estimating Equations (GEE) model. • GEE modelling will only be performed if at least 30% response rate at Day 85 for any one treatment group. • The model will be fitted using an unstructured covariance structure of the correlated responses. • Terms fitted in the GEE model will include: 
 
 Fixed Categorical	: Treatment group, Visit, Treatment group * Visit Interaction	
 
 Repeated	: Visit	
 
 	Fixed Categorical	: Treatment group, Visit, Treatment group * Visit Interaction	Repeated	: Visit
Fixed Categorical	: Treatment group, Visit, Treatment group * Visit Interaction			
Repeated	: Visit			
Model Results Presentation				

 • Binary endpoints will be summarised using counts and proportions of participants achieving a response by treatment group. • Point estimates and corresponding 95% confidence intervals will be constructed using contrasts for the treatment group by visit interaction. • Plots of the point estimates and 95% confidence intervals from the model will be generated for each treatment group by time. • If a minimum 30% response rate at Day 85 for any one treatment group is not achieved, the display should be created with 'Insufficient data to produce GEE analysis' printed in the main body of the display. 				

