Study Duration and Dosing	
 Each participant will participate in the study for approximately 20 weeks. This includes a screening period up to 30 days, an 84-day (12 week) treatment period, and a 28-day follow-up period after the last dose. Within 30 days of the screening visit (defined as day of consent signing), eligible participants enter a 2-part treatment phase as follows with study treatment starting on study day 1: 
 Part A: Approximately 36 participants are randomly assigned to receive either GSK2982772 60 mg three times daily (TID) or placebo TID for 42 days (6 weeks) in a 2:1 ratio. Part B: All participants who complete Part A move on to receive open label treatment of GSK2982772 60 mg TID for an additional 42 days (6 weeks). Treatment duration is a total of 84 days (12 weeks) inclusive of Parts A and B. Participants are followed-up for 28 days (4 weeks) after the last dose in Part B. Prior to amendment 01 being effective in each country, participants were randomly assigned to receive either: 
 Part A: GSK2982772 60 mg two times daily (BID) or placebo BID for 42 days (6 weeks) in a 2:1 ratio. Part B: Open label treatment for all participants who have completed Part A of GSK2982772 60 mg BID for an additional 42 days (6 weeks). 																															
Time & Events	
 Refer to Appendix 2: Schedule of Activities. During the 84-day (12 week) treatment period, participants attend the clinical for visits on Days 1, 15, 29, 43, 57, 71 and 85. At specific visits, participants must not take treatment prior to their scheduled treatment. On Days 8, 22, 36, 50, 64 and 78 participants were to be contacted by telephone and asked about their general health. Participants are given a diary card at every visit and asked to record daily study 																															

Overview of Study Design and Key Features	
	medication, concomitant medication and adverse events.

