5. CONSIDERATIONS FOR DATA ANALYSES AND DATA HANDLING CONVENTIONS

5.1. Study Treatment & Sub-group Display Descriptors

One subject was randomised to a BID regimen before the protocol was amended. Per instructions in the protocol, data will be summarised in tables and figures by treatment (GSK2982772 60mg or Placebo) irrespective of dosing regimen received (BID or TID). Data will be listed per treatment and dosing regimen received (BID or TID). Some key safety endpoints will be summarised by both randomised treatment and period treatment, details are provided in [Appendix 9](#).

Should a participant receive the wrong medication at any point during the study in error, that participant will be treated as having received GSK2982772 60mg TID for the duration of the study.

Randomised Treatment Group Descriptions					
RandAll NG		Data Displays for Reporting			
Code	Description	Description in tables/non-PK figures	Order in TF	Description in Listings/PK figures	Order in Listing
A	GSK2982772 60mg BID (Double-blind)	GSK2982772 60mg	2	GSK2982772 60mg BID	3
C	GSK2982772 60mg TID (Double-blind)	GSK2982772 60mg	2	GSK2982772 60mg TID	4
P	Placebo BID (Double-blind)	Placebo	1	Placebo BID	1
Q	Placebo TID (Double-blind)	Placebo	1	Placebo TID	2

Period Treatment Group Descriptions					
RandAll NG		Data Displays for Reporting			
Code	Description	Description in tables	Order in TF	Description in Listings	Order in Listing
A	GSK2982772 60mg BID (Double-blind)	GSK2982772 60mg	2	GSK2982772 60mg DB BID	3
B	GSK2982772 60mg BID (Open-label)	GSK2982772 60mg	2	GSK2982772 60mg OL BID	5
C	GSK2982772 60mg TID (Double-blind)	GSK2982772 60mg	2	GSK2982772 60mg DB TID	4
D	GSK2982772 60mg TID (Open-label)	GSK2982772 60mg	2	GSK2982772 60mg OL TID	6
P	Placebo BID (Double-blind)	Placebo	1	Placebo DB BID	1
Q	Placebo TID (Double-blind)	Placebo	1	Placebo DB TID	2

Treatment comparisons will be displayed as follows using the descriptors as specified:

- GSK2982772 60mg vs Placebo.

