12.10.8. Efficacy Figures

Efficacy: Figures					
No.	Population	IDSL / Example Shell	Title	Programming Notes	Deliverable [Priority]
Mayo					
2	Safety	EFF_F1	Individual Subject Profiles for Subjects Achieving Mayo Endoscopy Remission, Total Mayo Score, Partial Mayo Score, 3-domain Mayo Score, Mayo Clinical Response, 3-domain Mayo Clinical Response, Mayo Clinical Remission and 3-domain Clinical Remission over Time (Parts A and B) by Randomised Treatment	Separate pages for each endpoint.	IA SAC [1], SAC [1]
2	Safety	EFF_F4	Proportion of Subjects Achieving Mayo Endoscopy Remission and over Time (Parts A and B) by Randomised Treatment	Line graph with randomised treatment on the same plot	IA SAC [1], SAC [1]
2.3.	Safety	EFF_F3	Odds Ratio and 95% CI for Proportion of Subjects Achieving Mayo Endoscopy Remission (Parts A and B) by Randomised Treatment	GEE modelling will only be performed if at least 30% response rate at Day 85 for any one treatment group.	IA SAC [1], SAC [1]

Efficacy: Figures					
No.	Population	IDSL / Example Shell	Title	Programming Notes	Deliverable [Priority]
2.4.	Safety	EFF_F4	Proportion of Subjects Mayo Clinical Response, 3-domain Mayo Clinical Response, Mayo Clinical Remission and 3-domain Clinical Remission over Time (Parts A and B) by Randomised Treatment	Separate pages for each endpoint. Line graph with randomised treatment on the same plot.	IA SAC [1], SAC [1]
2.5.	Safety	EFF_F3	Odds Ratio and 95% CI for Achieving Mayo Clinical Response, 3-domain Mayo Clinical Response, Mayo Clinical Remission and 3-domain Clinical Remission over Time (Parts A and B) by Randomised Treatment	Separate pages for each endpoint. GEE modelling will only be performed if at least 30% response rate at Day 85 for any one treatment group.	IA SAC [1], SAC [1]
2.6.	Safety	EFF_F2	Mean (\pm SE) Total, Partial and 3-domain Mayo Scores over Time (Parts A and B) by Randomised Treatment	Separate pages for each endpoint.	IA SAC [1], SAC [1]
2.7.	Safety	EFF_F3	Point Estimates and 95% CI of Change from Baseline in Total, Partial and 3-domain Mayo Scores over Time (Parts A and B) by Randomised Treatment	Separate pages for each endpoint. Grey dashed line at y=0.	IA SAC [1], SAC [1]

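### Whether the Day 43 odds ratio is produced for the binary endpoints, at their only placebo-controlled visit, depends on a 30% response rate at Day 85, when both arms have had open-label drug

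*SAP*

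**What the plan says.** SAP section 8.1.2.1.2 lists Mayo endoscopy remission, Mayo and 3-domain clinical response and remission, and UCEIS remission. Each is assessed at Day 43 pre-dose and at Day 85. A single GEE model with treatment, visit and their interaction gives the estimates for both visits by contrasts. The condition for fitting it is: "GEE modelling will only be performed if at least 30% response rate at Day 85 for any one treatment group". If it fails, the display carries only the text "Insufficient data to produce GEE analysis". What always remains is descriptive: "Binary endpoints will be summarised using counts and proportions of participants achieving a response by treatment group".

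The condition is repeated in the programming notes of the GEE tables (12.10.7), the odds-ratio figures (12.10.8) and the raw-output listings (12.10.14). The effect measure is an odds ratio; Figure 2.3, for example, is titled "Odds Ratio and 95% CI for Proportion of Subjects Achieving Mayo Endoscopy Remission (Parts A and B) by Randomised Treatment".

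On design, section 2.3 says: "All participants who complete Part A move on to receive open label treatment of GSK2982772 60 mg TID". Section 8.1.2 keeps the randomised grouping throughout: "All efficacy data will be summarised for Parts A, B and Follow-up (if applicable) by randomised treatment".

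On labels, section 5.1 says "Treatment comparisons will be displayed as follows using the descriptors as specified" and then gives one descriptor, GSK2982772 60mg versus Placebo.

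**The concern.** For these endpoints Day 43 is the only visit at which the two arms differ as drug against placebo. By Day 85 both arms have had 42 days of open-label GSK2982772. The fitting rule looks only at Day 85, and this can go wrong in two ways.

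- **The rule is not met although Day 43 is informative.** No interval is produced for the randomised contrast. Only counts and proportions by arm remain.
- **The rule is met although Day 43 is sparse.** It can be met through the former placebo arm alone. If the placebo arm had no responders at Day 43, the odds ratio has no finite estimate. The binary section gives no fallback, whereas the section on continuous endpoints does provide alternatives.

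At stake is the interval for the only randomised estimate of endoscopic remission, clinical response and remission, and UCEIS remission.

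A smaller, related point is the fixed label. It also covers contrasts after Day 43, when nobody is on placebo: Day 85 for every endpoint, and Days 57 and 71 as well for FCP ("Change from baseline in Log-transformed FCP at Day 15, Day 29, Day 43, Day 57, Day 71 and Day 85").

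**Working it through.** The SAP gives no expected response rates and no power figure for these endpoints, so there is no figure of its own to reproduce. Response rates below are assumptions, shown over a range.

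**Inputs.** About 36 participants randomised 2:1 (section 2.3), taken as 24 and 12 with no dropout. Threshold 30% at Day 85 in either arm (8.1.2.1.2).

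**Step 1: the threshold in counts.** 0.30 × 24 = 7.2, so 8/24 is needed (7/24 = 29.2% fails). 0.30 × 12 = 3.6, so 4/12 is needed (3/12 = 25% fails).

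**Step 2: chance that the rule is met.** With independent arms and the same Day 85 rate in both,

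P(met) = 1 − P(X₂₄ ≤ 7) × P(Y₁₂ ≤ 3).

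At 25%: P(X₂₄ ≥ 8) = 0.2338 and P(Y₁₂ ≥ 4) = 0.3512, so P(met) = 1 − 0.7662 × 0.6488 = 0.503. Over the range:

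| Day 85 rate, both arms | 15% | 20% | 25% | 30% | 35% | 40% |
|---|---|---|---|---|---|---|
| P(met) | 0.11 | 0.28 | 0.50 | 0.72 | 0.88 | 0.96 |

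No Day 43 quantity enters this.

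**Step 3: met only through the former placebo arm.** At 25%: 0.7662 × 0.3512 / 0.5029 = 0.54 of the occasions on which the rule is met.

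**Step 4: empty Day 43 placebo cell.** P(0/12) = (1 − p)¹² = 0.54, 0.28, 0.14 and 0.07 at p = 5, 10, 15 and 20%.

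**Step 5: both conditions together.** Joint simulation, 100,000 trials per scenario, latent within-person correlation 0.6. Estimable means at least one responder and one non-responder in each arm at Day 43. Without any rule this has probability [1 − (1 − pA)²⁴ − pA²⁴] × [1 − (1 − pP)¹² − pP¹²], where pA and pP are the Day 43 rates on active and placebo.

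| Day 43 active / Day 43 placebo / Day 85 both (%) | Estimable with no rule | Produced under the rule | Suppressed by the rule alone |
|---|---|---|---|
| 15/5/15 | 45% | 7% | 38% |
| 20/5/20 | 46% | 16% | 30% |
| 25/5/25 | 46% | 26% | 20% |
| 25/10/25 | 72% | 39% | 33% |
| 30/10/30 | 72% | 54% | 18% |
| 30/15/35 | 86% | 76% | 10% |
| 35/15/40 | 86% | 82% | 3% |
| 40/20/40 | 93% | 89% | 4% |

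The last column is the second minus the third, up to rounding and simulation error. At 25/5/25 the rule is met in 0.501 of trials and an estimate results in 0.264, so 1 − 0.264/0.501 = 47% of trials meeting the rule have an empty Day 43 cell. Correlations of 0, 0.3 and 0.8 give 0.233, 0.247 and 0.274 in place of 0.264.

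**Step 6: two worked datasets.**

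- *Rule not met.* Day 43 10/24 versus 0/12 (Fisher p = 0.015); Day 85 7/24 and 3/12. The SAP gives no interval. The Miettinen-Nurminen difference is 41.7 points (95% CI 13.9 to 61.4).
- *Rule met.* Day 43 6/24 versus 0/12; Day 85 8/24 and 4/12. A logit GEE with treatment by visit, fitted with an independence working correlation, returns a Day 43 odds ratio of 1.6 × 10¹⁰ with a CI from 0 to infinity. Miettinen-Nurminen gives 25.0 points (−1.9 to 45.2). The SAP specifies an unstructured correlation. With complete data the treatment-by-visit model has one mean per arm and visit, so the fitted proportions equal the observed ones under either choice and 0/12 still has no finite log odds.

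**The case against.** The strongest reply is that little depends on this. The primary objective is safety, no formal hypotheses are planned, arm comparisons are made only if appropriate (section 2.4), and Table 6 marks every modelled efficacy analysis as conditional. A minimum-response rule is a sensible guard against unstable GEE output. Day 43 proportions are always shown, so a reader can compute an interval. The MMRM contrasts on the Mayo and UCEIS scores are not subject to the rule. Section 8.2.2 also allows a Bayesian interval on a remission rate.

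Most of this stands as a limit on importance. It does not rescue the rule: a guard set at Day 85 does not screen the Day 43 cells it would need to protect. The Bayesian interval is optional, post hoc and not a between-arm contrast.

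Two objections to the size also carry weight. The response rates are assumed, and six of the eight scenarios set the Day 85 rate equal to the Day 43 active rate. And at 25/5/25 the larger loss is plain sparseness: 100 − 26 − 20 = 54% of trials have no estimable Day 43 odds ratio under any rule. Only the last column of the Step 5 table is due to the Day 85 condition.

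A cell-count condition would admit weak estimates: 6/24 versus 1/12 gives an odds ratio of 3.7 with a Wald 95% CI of 0.4 to 35. That is true, but the width of the interval shows the weakness openly.

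On the label, the displays are titled by randomised treatment and the open-label switch is stated in the SAP, so the risk of misreading is small. It is still inaccurate after Day 43.

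**Conclusion.** The concern holds. The rule ties the only randomised contrast for the binary endpoints to later, uncontrolled data, and it leaves the Day 43 cells unchecked. Suppression by the rule alone ranges from 38% to 3% of trials across the assumed scenarios. It is largest when Day 85 rates are low and nearly vanishes at 40%. These figures assume a 24:12 split, no dropout and a latent correlation of 0.6. The structural point needs none of these assumptions. The rule applies endpoint by endpoint and leaves the MMRM analyses untouched. Because the endpoints are secondary or exploratory, serve estimation only and are always described by proportions, the change is advisable but low in priority.

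**What to change.** 1. For every binary endpoint, always report the Day 43 difference in proportions with a 95% CI that is valid with zero cells (for example Miettinen-Nurminen or exact unconditional), regardless of Day 85. This gives an interval in every trial and settles the main point by itself.
2. Replace the 30% Day 85 condition by a cell-count condition applied to the visit being contrasted: at least one responder and one non-responder per arm at that visit. If only Day 85 fails, estimate the Day 43 odds ratio from Day 43 data alone. The Day 43 odds ratio would then be estimable in 45% to 93% of trials over the same scenarios (46% at 25/5/25).
3. Label between-arm contrasts after Day 43 as early versus delayed start of GSK2982772: Day 85 for all endpoints, and also Days 57 and 71 for FCP.

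The cost is SAP wording, matching programming notes in 12.10.7, 12.10.8 and 12.10.14, and one extra table per binary endpoint. No new data are needed.

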Treatment Assignment	
 • At Screening a unique CRF number (Subject Number) is assigned. • Participants who meet screening eligibility criteria and complete pre-treatment assessments are randomised through an Interactive Response Technology System (IRTS). The IRTS confirms the participant's CRF number (Subject Number) and provides the randomisation number. • The randomisation number is generated by Clinical Statistics, prior to the start of the study, using validated internal software. Once assigned, this randomisation number must not be reassigned to any other participant in the study. • The randomisation is centrally controlled by the IRTS. • Approximately 36 participants were randomised in a 2:1 ratio to receive GSK2982772 60mg TID or Placebo TID in Part A. • Any participant that is re-screened outside of the allowed screening window at the approval of the GSK Medical Monitor, must be assigned a new unique Subject Number.

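### The binary-endpoint GEE is run without checking for empty arm-by-visit cells, so with no placebo responders at Day 43 the planned odds ratio and its interval do not exist and no fallback is named

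*SAP*

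**What the plan says.** Section 8.1.2.1.2 of the SAP states: "Binary efficacy endpoints will be statistically analysed using a Generalised Estimating Equations (GEE) model". The fixed terms are "Treatment group, Visit, Treatment group * Visit Interaction", with no covariate, and "The model will be fitted using an unstructured covariance structure of the correlated responses". For the results, "Point estimates and corresponding 95% confidence intervals will be constructed using contrasts for the treatment group by visit interaction".

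The section names no link function. The figure titles in Section 12.10.8 give the effect measure. Figure 2.3, for example, is "Odds Ratio and 95% CI for Proportion of Subjects Achieving Mayo Endoscopy Remission (Parts A and B) by Randomised Treatment", and Figures 2.5 and 2.26 also show odds ratios, as do the PP and PP + Completers versions of Figures 2.3 and 2.5. A logit link is therefore inferred.

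Whether the model is fitted rests on one condition: "GEE modelling will only be performed if at least 30% response rate at Day 85 for any one treatment group". If it is not met, "the display should be created with 'Insufficient data to produce GEE analysis' printed in the main body of the display". No other alternative output is described for binary endpoints. The alternative covariance structures and non-parametric analyses in Section 8.1.2.1.1 belong to the MMRM for continuous endpoints.

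On size, Section 2.3 says: "Approximately 36 participants were randomised in a 2:1 ratio to receive GSK2982772 60mg TID or Placebo TID in Part A". That is about 24 against 12.

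**The concern.** The condition looks at Day 85 only, and one arm is enough to satisfy it. By then everyone who completed Part A has been on open-label GSK2982772 (Section 2.3), so it carries little information about the placebo count at Day 43. It does not ask whether any arm-by-visit cell has no responders, or only responders.

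With a logit link and a free parameter for each cell, an empty cell has log odds of minus infinity. Day 43 is the only placebo-controlled comparison of the two arms. Mayo endoscopy subscore of 0 or 1, clinical response and clinical remission at that visit are named secondary endpoints (Section 2.2). Of the six binary endpoints in Section 8.1.2.1.2, four are remission endpoints, where low placebo counts are most plausible. If the model fails there, the substitute method would be chosen after the unblinded data had been seen.

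**Working it through.** The SAP gives no response rate, power statement or effect size for these endpoints, so there is no planned figure to reproduce beyond the split: 36 × 2/3 = 24 and 36 × 1/3 = 12.

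**1. What the model estimates.** Two arms × two visits give four cells. Intercept, treatment, visit and interaction give four parameters. With complete data the fitted values are the four observed proportions, and the Day 43 log odds ratio is logit(active) − logit(placebo).

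- Illustrative 8/24 v 1/12: ln(8/16) − ln(1/11) = −0.693 + 2.398 = 1.70. SE = √(1/8 + 1/16 + 1/1 + 1/11) = 1.13. The 95% CI for the odds ratio is exp(1.70 ± 1.96 × 1.13), or 0.60 to 50.4. This is wide but finite.
- Illustrative 8/24 v 0/12: ln(0/12) is minus infinity. There is no finite odds ratio and no Wald interval.

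**2. What software does with it.** A binomial-logit GEE was fitted in Python (statsmodels) to Day 43 counts of 8/24 v 0/12 and Day 85 counts of 10/24 v 4/12, which meet the 30% condition. All counts are illustrative. Convergence was reported each time.

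| Working correlation | Day 43 log OR | Robust SE |
|---|---|---|
| Independence | 23.9 | not computable |
| Exchangeable | 30.9 | 4.9 × 10^5 |
| Unstructured (as planned) | 30.9 | 4.1 × 10^5 |

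These are stopping values, not estimates. Under the unstructured choice the Day 85 contrast was damaged too: robust SE 61.6 against 0.74 model-based. With no placebo responders at either visit, a fit returned a robust SE of 0.43 and an odds-ratio interval of about 3 × 10^10 to 1 × 10^11, which is falsely tight.

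**3. How often the problem can arise.** Two things must both happen.

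- Empty placebo cell at Day 43: (1 − p)^12, where p is the true placebo rate. This is 0.540, 0.282 and 0.142 for p = 5%, 10% and 15% (assumed).
- Condition met at Day 85: at least 8/24 or at least 4/12. For a common Day 85 rate q, the probability is 1 − P(X24 ≤ 7) × P(X12 ≤ 3). At q = 30% this is 1 − (1 − 0.435)(1 − 0.508) = 0.722. At q = 10%, 20% and 40% it is 0.027, 0.276 and 0.957.

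Multiplying the two, with the visits taken as independent:

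| Day 85 rate, both arms | p = 5% | p = 10% | p = 15% |
|---|---|---|---|
| 10% | 1.5% | 0.8% | 0.4% |
| 20% | 15% | 8% | 4% |
| 30% | 39% | 20% | 10% |
| 40% | 52% | 27% | 14% |

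Independence is an assumption. If placebo participants' responses at the two visits are positively correlated, an empty Day 43 cell makes it harder for that arm to reach 4/12 at Day 85. Counting only the active arm's route at q = 30% gives 0.435 × 0.540 = 24%, 0.435 × 0.282 = 12% and 0.435 × 0.142 = 6%.

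**4. What the same data can support.** For 8/24 v 0/12 the risk difference is 8/24 − 0/12 = 33.3 percentage points. The 95% CI is 6 to 54 (Miettinen-Nurminen) or 4.6 to 53.3 (Newcombe). Fisher's exact two-sided p is 0.033, and the exact conditional odds-ratio interval runs from 1.01 to infinity.

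**The case against.** The case for leaving the plan alone has real content.

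- **Efficacy is secondary and conditional.** The primary objective is safety, with no formal hypothesis. Section 2.4 makes efficacy comparisons only if appropriate, and Table 6 marks these models as conditional. No decision rule in the SAP rests on the odds ratio. This stands, and it limits the severity.
- **The data are still shown.** Counts, proportions, proportion-over-time figures and listings are produced whether or not the GEE runs. A reader would see 8/24 v 0/12. This stands: only the between-arm interval is lost.
- **An empty cell is not enough.** A reader might take the 54%, 28% and 14% chances of 0/12 as the chance of failure and conclude that breakdown is likely. The documents do not support that. They give no placebo rate, and the Day 85 condition must also be met. When it is not, the planned text appears and no meaningless interval is printed. Clinical response endpoints also give less reason to expect empty cells than remission does.
- **The example is not a clear win.** A reader might infer that a decisive drug effect would be hidden. With p = 0.033 and an exact lower limit of 1.01, 8/24 v 0/12 is borderline.
- **The software evidence is indirect.** The SAP uses SAS, and the fits here did not. The printed values are software-specific. That no finite odds ratio exists does not depend on software.
- **The link is inferred.** The display specifications are available only on request. Still, the planned effect measure is an odds ratio, and it has no finite estimate when the placebo cell is empty.

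None of these points supplies a cell check or a fallback.

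**Conclusion.** The point holds as a gap that should be closed before unblinding; it does not threaten the trial's primary objective. As written, the 30% condition can let the GEE run when the placebo Day 43 cell is empty. The planned odds ratio and interval for the placebo-controlled comparison then do not exist, the insufficient-data text is not triggered, and nothing is named in its place.

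The joint chance runs from 0.4% to 52% over assumed placebo Day 43 rates of 5% to 15% and Day 85 rates of 10% to 40%. At 30% on Day 85 it is about 39%, 20% and 10%. These figures assume 24 v 12 with complete data, equal Day 85 rates in the two arms and independent visits. The algebraic result assumes only the logit link implied by the odds-ratio displays.

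A reader might infer that the GEE should be dropped or always made supportive. The defect does not require that. Where every cell has both outcomes, the model gives a finite result.

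**What to change.** In Section 8.1.2.1.2:

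1. For each binary endpoint, pre-specify the Day 43 risk difference, GSK2982772 minus placebo, with a Miettinen-Nurminen or Newcombe 95% CI. Name one of the two, and report it whatever the cell counts.
2. Report the GEE odds ratio only when every arm-by-visit cell has at least one responder and one non-responder, in addition to the existing 30% condition.
3. When the cell check fails, show the risk difference in the odds-ratio displays: Figures 2.3, 2.5 and 2.26, the PP versions (2.10 and 2.12) and the PP + Completers versions (2.17 and 2.19). Give the matching GEE tables in Section 12.10.7 the same rule.
4. State the link function.

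The cost is a few lines of SAP text and one extra standard procedure per endpoint, with no new data. The risk difference is a per-visit estimate and does not use the within-participant correlation. With complete data that correlation adds nothing to the Day 43 estimate, because the model has a free parameter for every cell.
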